4.6.3 PET/MRI Imaging Interpretation and Storage

Images from the PET/MRI will be stored and reviewed using a commercially available software package (MIM Encore, Cleveland, OH) and not be available for viewing in the institutional PACS or patient's medical record. This is in an effort to blind the treating physicians from making clinical decisions on an experimental imaging technique. The prostate MRI images will be sent to clinical PACS and the medical record as part of standard-of-care imaging and can be used in the clinical-decision making process. No formal interpretation will be generated for the [¹⁸F]fluciclovine-PET portion of the PET/MRI study, but the prostate MRI will have a clinical interpretation by a dedicated abdominal radiologist who will also be blinded to the patient enrollment in the study. Dedicated study readers from both abdominal imaging and molecular imaging will interpret first the prostate MRI alone, and then the fused PET/MRI to assess potential added value from the PET/MRI. The study readers will be blinded to the results of any additional standard-of-care imaging and clinical evaluation and will only have knowledge that the patient has biopsy-proven prostate cancer.

mpMRI images acquired from the fluciclovine-PET/MRI study will be scored initially without access to the fluciclovine-PET portion of the study using the method described below. Once the results of the MR only portion of the study have been recorded, the same reader will be given access to the entire study and provide a second set of scores for the combined PET/MRI images. The concordance for metastases in lymph node stations will be determined from these scores. At least two readers will score each study, and discrepancies will be recorded and resolved through a consensus read after finalizing individual scoring.

MRI Data Analysis: The MRI images will be qualitatively analyzed.

Qualitative analysis: A visual evaluation of the pelvic lymph nodes with suspected metastatic disease will be performed. The number of positive metastatic lymph nodes and their nodal stations will be recorded. Nodal stations that will be examined include right and left common iliac, internal iliac, external iliac, obturator, inguinal, and retroperitoneal (total of 11 stations per patients).

T1/T2 Images

0 = Normal lymph nodes

1 = Mild prominence not meeting RECIST criteria for adenopathy (low suspicion)

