2 = Definitely abnormal size or morphology, possible metastasis (intermediate suspicion)

3 = Markedly abnormal size and morphology, likely metastasis (high suspicion)

DWI Images

0 = Normal diffusion

1 = Low level of diffusion restriction when compared to adjacent normal appearing lymph nodes (low suspicion)

2 = Slightly higher level of diffusion restriction when compared to adjacent normal appearing lymph nodes (intermediate suspicion)

3 = Definitely higher level of diffusion restriction when compared to adjacent normal appearing lymph nodes (high suspicion)

Note: In cases of nonhomogenous intensity on DWI and ADC images, the grade will be determined on the basis of the most suspicious area.

PET Data Analysis: The PET images will be qualitatively and quantitatively assessed. The scoring will be based primarily on the PET data, but the reader will have access to the MRI data for anatomic correlation and characterization of lymph node morphology. For PET data analysis, a lymph node positive based on MRI criteria but negative based on fluciclovine-PET criteria will be scored as negative.

Qualitative analysis: A visual evaluation of the pelvic lymph nodes with suspected metastatic disease will be performed. As per manufacturer guidelines, lymph nodes measuring less than 1 cm in short-axis dimension will be compared to blood pool tracer activity. For lymph nodes measuring greater than 1 cm, comparison of activity will be made to the activity in the bone marrow of the L3 vertebral body. The number of positive metastatic lymph nodes and their nodal stations will be recorded.

0 = No uptake or uptake lower than appropriate reference (blood pool vs. L3 marrow)

1 = Uptake equal to reference (low suspicion)

2 = Uptake slightly greater than reference (intermediate suspicion)

3 = Uptake definitely greater than reference (high suspicion)

Quantitative analysis: Nodes scored as intermediate or high suspicion based on MRI and/or PET will undergo further quantitative analysis.

Standardized uptake values (SUVs): The maximum SUV will be measured. Additionally, the mean SUV and metabolic tumor volume will be measured based on a 40% isocontour.

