Lesion to blood pool and marrow ratios: Tissue SUV is a simple uptake ratio of activity in an area of interest compared to a normalized tissue background level. As stated in section B, activity in lymph nodes measuring less than 1 cm in short-axis dimension will be compared with activity in the blood pool and a lesion:blood pool activity ratio will be calculated. For lymph nodes measuring greater than 1 cm in short-axis dimension, activity will be compared to activity in the L3 vertebral body marrow and a lesion:marrow activity ratio will be calculated..

Dynamic PET analysis: Time-activity curves (TACs) will be generated for pelvic lymph nodes scored as intermediate or high suspicion on visual analysis. Additionally, TACs will be generated for three reference pelvic lymph nodes scored as normal. The maximum SUV at peak fluciclovine uptake, the time to peak, and the shape of the TACs over the 8 min dynamic acquisition (rising, plateau, washout) will be recorded. This analysis is exploratory as the role of dynamic fluciclovine-PET for the initial staging of prostate cancer is not established.

KEY ANALYSIS FOR SPECIFIC AIM 1

Based on the consensus PET and MRI scoring, the total percentage of nodal scoring discrepancies will be calculated. Although the total number of patients is small, a total of 165 pelvic nodal stations will be examined. In this pilot study, a discrepancy between MR-only and fluciclovine-PET/MR greater than 10% would motivate a larger study with more rigorous references standards including histopathology.

KEY ANALYSIS FOR SPECIFIC AIM 2

This study will use the nomograms routinely used by the UAB urology service in assessing newly diagnosed prostate cancer. The use of nomograms is necessary, as we will not routinely obtain histopathological verification in these high-risk, nonoperative patients in this study. Expected frequencies of lymph node metastases based on patient risk factors will be compared to observed frequencies of lymph node metastases in specific aim 1 on mpMRI alone, fluciclovine-PET/MRI, and assuming that discrepant nodes between imaging modalities (i.e. positive on one, negative on other) will be counted as positive, a combination of the two modalities that includes discrepant nodes. The assessment that most closely matches the expected frequency based on the nomogram will be considered most accurate, although small sample size will require larger studies for confirmation.

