6.4 Analysis

Since this is a single arm exploratory pilot study, where no formal power calculations were performed for the study's sample size, this study will largely be exploratory and descriptive. For all clinical and histological evaluations, as well as imaging parameters (SUV), we will generate summary tabulations of the number of observations, mean, standard deviation, median, minimum, and maximum for continuous variables, and the frequency and percentage for categorical variables. Analyses will be primarily descriptive and graphical in nature whereas the proposed sample size for the study limits the distributional assumptions of certain analyses. Therefore, non-parametric approaches will

be considered. For specific aim 1, in order to correlate imaging parameters between imaging modalities our correlation analysis will be performed using Spearman's Rank correlation and Wilcoxon signed-rank sum tests. In order to address specific aim 2, to compare observed frequencies of metastases and expected frequencies, a Chi-squared analysis will be performed. Given the small sample size, a Yates' correction may be utilized. Due to the small sample size and potential for sparse data, we may use Firth's penalized likelihood approach. Data transfer, management, and analyses will be performed using Excel and SAS v9.4.

6.4.1 Analysis for Primary Endpoints and Specific Aim 1: The imaging data from [¹⁸F]fluciclovine PET/MRI or mpMRI will be categorized from 0 to 3 indicating likelihood of having metastasis as '0' indicating no sign of metastasis and >0 indicating there is sign of metastasis. The number and percentage of metastasis identified by either [¹⁸F]fluciclovine PET/MRI or mpMRI will be calculated along with exact 95% CI using Clopper-Pearson method. The agreement and concordance of using these two imaging results will be evaluated with McNemar test due to correlated results from same patients when the result is dichotomized as yes or no, or using Spearman's Rank correlation analysis when the result is measured as 0-3.

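### Section 6.4.1 counts every score above 0 as a sign of metastasis, although section 4.6.3 labels score 1 low suspicion on all three reading scales

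*Combined protocol and SAP*

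**What the plan says.** Section 6.4.1 of the combined protocol and SAP places each modality's result on a 0-3 scale and splits it with 0 "indicating no sign of metastasis and >0 indicating there is sign of metastasis". The next sentence gives the number and percentage of metastasis per modality with an exact (Clopper-Pearson) 95% CI. The one after that gives a McNemar test for the result as yes or no, and a Spearman correlation for the 0-3 score.

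Section 4.6.3 defines the scores. Score 1 reads:

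- PET: "1 = Uptake equal to reference (low suspicion"
- T1/T2: "1 = Mild prominence not meeting RECIST criteria for adenopathy (low suspicion"
- DWI: "1 = Low level of diffusion restriction when compared to adjacent normal appearing lymph nodes (low suspicion"

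On the T1/T2 scale the word metastasis first appears one step higher: "2 = Definitely abnormal size or morphology, possible metastasis (intermediate suspicion".

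Section 4.6.3 also tells readers, for MRI and again for PET, that "The number of positive metastatic lymph nodes and their nodal stations will be recorded". In the PET rules, "a lymph node positive based on MRI criteria but negative based on fluciclovine-PET criteria will be scored as negative". Neither instruction says which score makes a node positive.

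For Aim 2, the key analysis in section 4.6.3 says that nomogram expectations "will be compared to observed frequencies of lymph node metastases in specific aim 1". It states no cut of its own.

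**The concern.** The analysis cut does not fit the labels of the scale it is applied to. Under >0, three kinds of read enter the percentage of metastasis: a node whose uptake does not exceed its reference, a node that misses the size criterion named in the scale, and a node with only a low level of restriction. No reason is given for so broad a cut.

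Section 6.2 makes the percentage of men with detectable metastasis the primary endpoint, so its definition decides what the main estimate means. Aim 2 takes its observed frequencies from Aim 1 and calls the reading closest to the nomogram the most accurate. A cut that raises the observed frequencies could change which reading that is.

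The reader instructions leave a second opening. Because section 4.6.3 does not define a positive node, a score-1 node could be left out of the recorded positive nodes and still be counted as metastasis under section 6.4.1.

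**Working it through.** **Inputs from the plan.** n = 15; 11 stations per man; expected detection 30% for PET/MRI and 20-25% for mpMRI (sections 6.2 and 4.6.3).

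**Step 1: the plan's own figures.** Clopper-Pearson limits are Beta(0.025; x, n-x+1) and Beta(0.975; x+1, n-x), with x = 15p. For 20%, 25% and 30% (x = 3, 3.75, 4.5) they are 4.3-48.1%, 6.9-53.4% and 9.7-58.4%. The table in section 6.2 is reproduced. The arithmetic is sound; the question is what counts as an event.

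**Step 2: the weight of one man.** 1/15 = 6.7 points. The planned gap is (0.30 - 0.25) x 15 = 0.75 men to (0.30 - 0.20) x 15 = 1.5 men. One man more moves the interval from 7.8-55.1% (4/15) to 11.8-61.6% (5/15).

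**Step 3: illustration of the cut.** The documents give no frequency of score 1, so three things are assumed: a share f of stations in otherwise negative men scores 1; any positive station makes the man positive; f is the same in both modalities. Let q be the chance that such a man has at least one score-1 station.

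- Independent stations: q = 1 - (1 - f)^11.
- Correlated stations: beta-binomial with 11 stations and ICC 0.3 (assumed).
- Percentage under >0: p + (1 - p)q, where p is the percentage at score 2-3.
- Gap under >0: (0.30 - 0.20)(1 - q).

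| f | q, independent / ICC 0.3 | 30% becomes | 20% becomes | 10-point gap becomes |
|---|---|---|---|---|
| 0.5% | 0.054 / 0.022 | 34% / 32% | 24% / 22% | 9.5 / 9.8 |
| 1% | 0.105 / 0.044 | 37% / 33% | 28% / 24% | 9.0 / 9.6 |
| 2% | 0.199 / 0.087 | 44% / 36% | 36% / 27% | 8.0 / 9.1 |
| 3% | 0.285 / 0.128 | 50% / 39% | 43% / 30% | 7.2 / 8.7 |
| 5% | 0.431 / 0.205 | 60% / 44% | 55% / 36% | 5.7 / 8.0 |

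Each modality's own percentage rises, which matters for a comparison with the 20-30% that section 6.2 takes from nomograms. The difference between modalities shrinks only modestly except at the highest rates. With unequal rates it could move further and in either direction, but the documents give no basis for choosing such rates.

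**The case against.** The strongest reply is that >0 is a choice and not an error. It is the only cut stated, and it is applied alike to both modalities. A sign of metastasis and low suspicion are not opposites. A sensitive cut also suits a study that hopes to find disease in subcentimeter nodes (section 2.0, Aim 1). This stands in part: no section names score 2 as the positivity threshold, and the PET scale rests on manufacturer guidelines that the documents do not reproduce. But section 6.4.1 goes on to report a percentage of metastasis, not of suspicion, and gives no reason for the broad cut.

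A reader might infer that the plan contains two conflicting cuts, because section 4.6.3 restricts quantitative and time-activity work to nodes of intermediate or high suspicion. The documents do not support that: the restriction only selects nodes for measurement.

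A reader might also infer that >0 biases the comparison towards one modality, or erases the expected difference. The documents support neither. The sensitivity to one man in step 2 comes from n = 15 and holds under any cut.

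The link from the >0 split to the McNemar test is by adjacency. It is the likely reading, since no other dichotomisation is given, but it is inferred.

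Finally, this is a descriptive pilot with planned intervals already 44 to 49 points wide, and an exact McNemar test would need six discordant pairs, all in one direction, to fall below 0.05 (p = 0.031). That limits the consequences. It does not remove the need for an interpretable primary percentage.

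**Conclusion.** The concern holds as a mismatch between the analysis cut and the scale's own labels. Low-suspicion reads count as detected metastases in the percentage and its exact CI, very probably in the McNemar test, and, through the Aim 1 frequencies, in the Aim 2 nomogram comparison.

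The size and direction of the effect on the PET/MRI versus mpMRI difference cannot be derived from the documents. Under the assumptions of step 3, a 10-point gap falls to about 6 to 10 points, while an expected 30% rises to between 32% and 60%. Those figures rest on an assumed score-1 rate, an assumed any-station rule and an assumed correlation.

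The Spearman analysis of the 0-3 score is unaffected, and the 10% discrepancy rule for Aim 1 states no cut. The plan should be changed, but the point does not undermine the study. How T1/T2 and DWI combine into one mpMRI score, and how stations give a result for the man, are separate gaps that exist under any cut and add no weight here.

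**What to change.** Before the reads are analysed, define a positive read once and use the same definition in section 4.6.3, section 6.4.1 and the Aim 2 comparison.

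In section 6.4.1, prespecify the percentage, exact CI and McNemar test at two cuts for both modalities: consensus score 2-3 (intermediate or high suspicion, the cut that fits the scale's labels) and score >0. Make score 2-3 the main result unless the sponsor documents a reason for >0. State explicitly that the McNemar test uses these cuts.

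In section 4.6.3, add one line saying which score makes a node positive when readers record positive nodes and when the PET rule overrides a positive MRI node.

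The cost is small, because the 0-3 scores are already recorded and either cut can be computed from them. It is not purely analysis wording, since the line in section 4.6.3 is a reader instruction. The main result will have the same number of positives or fewer in both modalities. Small nodes with uptake equal to reference, which bear on the subcentimeter aim, would appear only in the >0 analysis.

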6.0 Statistical Considerations

6.1 Study Design

This is a prospective pilot trial to determine the potential use of [¹⁸F]fluciclovine PET/MRI in the pretreatment staging and post-therapy follow-up of patients with high-risk prostate adenocarcinoma. The primary objective of this study is to determine the concordance of imaging findings for fluciclovine-PET/MRI and mpMRI of the pelvis and prostate gland. The secondary objective is to determine the correlation between organ-confined disease, lymph node metastases, extraprostatic extension, and seminal vesicle invasion on fluciclovine-PET/MRI with the expected frequencies of these metastases based on established nomograms and risk-prediction models.

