6.2 Sample Size Determination

This is a pilot study that may warrant a larger study with increased power to determine statistical significance if expected results are observed. We plan to enroll 15 patients, primarily determined by budgetary constraints and feasibility of patient recruitment in one year. No formal power calculations were used in the generation of the sample size. The primary end point of the study is to estimate percentage of high-risk prostate cancer patients whose metastasis can be detectable early by using of [¹⁸F]fluciclovine-PET/MRI comparing using standard care of mpMRI imaging. According to risk-prediction models and nomograms used in routine clinical practice, approximately 20-30% of patients with high-risk prostate adenocarcinoma will be diagnosed with nodal metastases. We expect that using [¹⁸F]fluciclovine PET/MRI will achieve similar results, e.g. 30% for early detection of metastasis without invasive procedures, and using mpMRI will result in less of detection of metastasis, e.g. 20%-25%. A size of 15 will provide a two-sided 95% confidence intervals (CI) for point estimate (% of metastasis) from 9.7% to 58.4% when the true estimate is 30% using Clopper-Pearson method. Table below shows the 95% CI when the true estimate varies.

Proportion (%) (estimate of metastasis)	Sample size	95% CI Lower limit	95% CI Upper limit
20	15	4.3	48.1
25	15	6.9	53.4
30	15	9.7	58.4

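### Section 6.4.1 evaluates concordance, the primary objective, with McNemar's test, which does not measure agreement; the station discrepancy percentage, which does, has no interval allowing for 11 stations per man

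*Combined protocol and SAP*

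**What the plan says.** Section 6.1: "The primary objective of this study is to determine the concordance of imaging findings for fluciclovine-PET/MRI and mpMRI". Section 5.1 also lists concordance among the primary endpoints. Section 6.2 words the primary end point differently: "The primary end point of the study is to estimate percentage of high-risk prostate cancer patients whose metastasis can be detectable early", compared with mpMRI. It expects about 30% positive on PET/MRI and 20-25% on mpMRI.

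Section 6.4.1 cuts the 0-3 score, with 0 "indicating no sign of metastasis and >0 indicating there is sign of metastasis". It then gives the method for yes/no results: "The agreement and concordance of using these two imaging results will be evaluated with McNemar test due to correlated results from same patients". Spearman's correlation is named for the 0-3 scores, and section 6.4 lists for Aim 1 Spearman's "Rank correlation and Wilcoxon signed-rank sum tests". The only interval in 6.4.1 is a Clopper-Pearson interval for the percentage found by each modality.

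Section 4.6.3 works at station level: "The concordance for metastases in lymph node stations will be determined from these scores". Its key analysis for Aim 1 says "the total percentage of nodal scoring discrepancies will be calculated", counts 165 stations, and treats a discrepancy above 10% as grounds for a larger study. No interval is attached to that percentage.

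**The concern.** McNemar's test compares marginal positive rates. It uses only the difference between the two discordant counts, relative to their sum, and takes no account of how many positives are shared. It suits the question whether PET/MRI finds more disease, which is Hypothesis 1 in section 2.0 and the end point as worded in 6.2. It does not answer the concordance question that 6.4.1 assigns to it. A non-significant result filed under agreement and concordance could be read as concordance when the readings barely overlap.

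The other named methods do not close the gap. Spearman's correlation responds to poor overlap, but it measures association and cannot see a systematic shift in scores. The Wilcoxon test can detect a shift but is not a measure of agreement. No kappa, and no positive or negative agreement, is named anywhere.

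The discrepancy percentage does measure agreement directly, being its complement. It is also the pilot's own criterion for going further. Without an interval, a reader may take 165 as the information content when there are only 15 independent men.

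**Working it through.** **Figures in the plan.** Clopper-Pearson limits are the 2.5% quantile of Beta(x, n-x+1) and the 97.5% quantile of Beta(x+1, n-x). With n=15 and x=15p, p = 20%, 25% and 30% give 4.3-48.1%, 6.9-53.4% and 9.7-58.4%, as in the 6.2 table. Stations: five paired plus one unpaired gives 5×2+1 = 11 per man, and 11×15 = 165, as in 4.6.3.

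**McNemar against agreement.** Take 5 PET/MRI-positive men (33%) and 3 mpMRI-positive men (20%) of 15, and let the shared positives fall from 3 to 0. Chance agreement is (5×3 + 10×12)/15² = 0.60. Kappa = (observed - 0.60)/0.40. Positive agreement = 2×shared/(5+3). The exact p is a two-sided binomial test on the discordant pairs. The asymptotic p is from (b-c)²/(b+c) without correction.

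| Shared | PET-only / MR-only | Agreement | Positive agreement | Kappa | Exact p | Asymptotic p |
|---|---|---|---|---|---|---|
| 3 | 2 / 0 | 13/15 = 87% | 75% | 0.67 | 0.50 | 0.16 |
| 2 | 3 / 1 | 11/15 = 73% | 50% | 0.33 | 0.63 | 0.32 |
| 1 | 4 / 2 | 9/15 = 60% | 25% | 0.00 | 0.69 | 0.41 |
| 0 | 5 / 3 | 7/15 = 47% | 0% | -0.33 | 0.73 | 0.48 |

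The paired difference is 2/15 = +13 points in every row. With 4 versus 3 positives the exact p is 1.00 at every overlap, while agreement falls from 14/15 (93%) to 8/15 (53%) and kappa from 0.81 to -0.30.

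**Spearman.** On the yes/no data of the table, Spearman falls 0.71, 0.35, 0.00, -0.35, so it does register lost overlap. For a score shift, take ten men scored 0 on both and five scored 1 on mpMRI and 3 on PET/MRI. Spearman is 1.00, yet exact score agreement is 10/15 = 67%. The mean observed score gap is 5×2/15 = 0.667. The gap expected by chance is (2/3)(1/3)×3 + (1/3)(2/3)×1 + (1/3)(1/3)×2 = 1.111. Linear weighted kappa is 1 - 0.667/1.111 = 0.40. Wilcoxon on these data gives exact p = 2×(1/2)⁵ = 0.06.

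**Discrepancy percentage.** 16/165 = 9.7% and 17/165 = 10.3%, so 17 is the smallest count above the trigger. The design effect is 1 + (11-1)×ICC, the effective n is 165 divided by it, and Clopper-Pearson is applied to the effective n. The documents give no intra-patient correlation (ICC), so the values are assumptions.

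| Assumed ICC | Design effect | Effective n | 95% interval for 10.3% |
|---|---|---|---|
| 0 | 1 | 165 | 6.1-16.0% |
| 0.1 | 2 | 82.5 | 4.7-19.0% |
| 0.2 | 3 | 55 | 3.7-21.5% |
| 0.3 | 4 | 41.25 | 3.0-23.8% |

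In a beta-binomial simulation (15 men, 11 stations each, true discrepancy 10%, 20,000 runs), a nominal 95% interval that treats stations as independent covers 96% at ICC 0, 87% at 0.1, 77% at 0.2 and 70% at 0.3.

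**Direction.** Seventeen discrepancies split 17-0, 0-17 or 9-8 all exceed 10%, with net differences of +10.3, -10.3 and +0.6 points for PET/MRI. The Aim 2 key analysis in 4.6.3 plans frequencies for mpMRI, for PET/MRI and for a combination counting every discrepant node as positive. PET-only = combination - mpMRI, and MR-only = combination - PET/MRI. For example, with 10 shared, 9 PET-only and 8 MR-only stations, the three counts are 18, 19 and 27, and 27-18 = 9 and 27-19 = 8.

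**The case against.** McNemar would not stand alone. Section 4.6.3 makes the discrepancy percentage the key analysis for Aim 1, and Spearman's correlation would usually expose poor overlap. A reader might infer that the plan intends to declare concordance from a non-significant McNemar result. No section says so; the risk lies in the label 6.4.1 gives the test.

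The worst rows of the table need few or no shared positives. That is unlikely when the same reader scores the MRI first and then has it available for the combined read. The near-constant p-values also depend on the exact test, which the plan does not specify. Both points are fair. The uncorrected asymptotic p is still non-significant in every row, and agreement already drops from 87% to 73% with one fewer shared positive.

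A reader might also infer that the plan hides whether PET/MRI added or removed positives. That goes too far. The frequencies planned for Aim 2 yield the split if they are reported per station at one cut, and section 5.2 lists added metastases as a secondary endpoint. What remains is that the unit is not stated and the split is not shown beside the 10% figure.

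Finally, this is a 15-man study declared exploratory, without a power calculation, and kappa will be very imprecise. This limits the consequence but does not make McNemar a measure of agreement.

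**Conclusion.** Wrong as written, in two respects. The method that 6.4.1 assigns to dichotomised agreement tests a different question: at the same marginal counts it stays non-significant while kappa runs from 0.67 to -0.33. The direct measure, with its 10% trigger, is reported without uncertainty. At the trigger the interval is 6.1-16.0% under independence and roughly 3-24% at an assumed ICC of 0.3.

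The agreement result follows from the definition of the test; the counts of 5 and 3 are illustrative, chosen near the 6.2 rates. The clustered widths rest on the assumed ICC.

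Three further points are matters of specification or presentation, not errors: the direction split, the cut to which the 10% rule applies, and whether McNemar is run per man or per station. The documents do not support calling McNemar useless here or the 10% trigger invalid. Because the study is descriptive, what suffers is the reading of the concordance result and of the trigger, not a confirmatory error rate.

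**What to change.** In 6.4.1:

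- Assign McNemar (exact, per patient), with the paired difference and its confidence interval, to the added-detection question in Hypothesis 1 and 6.2.
- State how the separate T1/T2 and DWI scores in 4.6.3 combine into one mpMRI score per station. No combining rule is given, and neither a paired table nor a weighted kappa can be built without one.
- For concordance, report the paired table and percent agreement with positive and negative agreement, and add kappa (weighted for the 0-3 scores) as a supplement.

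In 4.6.3:

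- Give the discrepancy percentage a 95% interval that accounts for clustering by patient, for example by resampling patients. With 15 clusters, simple methods can still undercover: a t-interval on patient means covered 84-94% in the same simulation for assumed ICC values from 0 to 0.5.
- Show PET-only and MR-only counts beside the total, at the same unit and cut, and state the cut to which the 10% rule applies. The trigger itself need not change.

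The cost is the protocol wording, one decision on combining the MRI scales, and modest analysis code; no new data are needed. The estimates will be imprecise: in the example, kappa of 0.67 has a patient-resampled 95% interval of about 0 to 1.
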